8.4 Censoring Rules

The censoring rules for PFS are explained in [Table 4](#), based upon investigator's tumor assessments and the FDA Guidance for Industry, *Clinical Trial Endpoints for the Approval of Cancer Drugs and Biologics* (2007).

For PFS2, if a subject did not have PD (solely based on the investigator-provided information on the Survival Status eCRF) after starting a new anticancer treatment, or did not die during the study, the subject will be censored on the date last known to be alive.

For OS, in the absence of confirmation of death, subjects will be censored either at the date last known to be alive or the date of data cutoff, whichever is earlier.

Table 4 Censoring Rules for Progression-Free Survival

No.	Situation	Date of Progression or Censoring	Outcome
1	No baseline or postbaseline tumor assessments	Date of randomization	Censored
2	Progression documented between scheduled visits	Date of first radiologic PD assessment	Progressed
3	No progression at the time of data cutoff	Date of last adequate radiologic assessment prior to or on date of data cutoff	Censored
4	New anticancer treatment started	Date of last adequate radiologic assessment prior to or on date of new anticancer treatment	Censored
5	Death before first PD assessment	Date of death	Progressed
6	Death between adequate assessment visits*	Date of death	Progressed
7	Death or progression after more than one missed visit** or after 28 days from the last dose of study treatment	Date of last adequate radiologic assessment before missed tumor assessments	Censored
8	Treatment discontinuation for reasons other than PD	Date of last radiologic assessment before treatment discontinuation	Censored

CR = complete response, PD = progressive disease, PR = partial response, SD = stable disease.

* Adequate tumor assessment is a radiologic assessment of CR, PR, SD, non-CR/non-PD or PD as determined by investigators.

** More than 1 missed visits is defined as having either 1 of the following 2 durations being longer than 18 weeks - 1 day, which is 125 days ($= ((8+1) \times 2 \times 7) - 1$) for subjects on the every-8-week tumor assessment schedule in this study:

- a. Duration between 2 consecutive tumor assessments
- b. Duration between the last adequate tumor assessment and death or PD

The priority of the censoring rules is as follows:

1. If the subject had PD or death, the following sequence will be applied:

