 - If a subject did not have a baseline tumor assessment (No. 1), the subject will be censored on the date of randomization. However, if the subject died within 125 days (18 weeks – 1 day) after randomization and did not receive new anticancer treatment, the date of death will be the PFS event date (not censored).
 - If a subject had new anticancer treatment before PD or death (No. 4), the subject will be censored on the date of the last tumor assessment prior to or on the start date of new anticancer treatment.
 - If PD is reported after the drug discontinuation visit, the subject will be censored at the date of last radiologic assessment before drug discontinuation except when PD occurred at the same visit as drug discontinuation (No. 8). If PD occurred within 4 weeks of drug discontinuation, it will be considered PD at the drug discontinuation visit and counted as a PFS event.
 - If a subject missed more than 1 assessment before PD or death (No. 7), the subject will be censored on the date of the last tumor assessment before PD or death. Note that if a subject is censored by both this criterion and the anticancer treatment criteria, the earliest censoring date will be used.
 - Otherwise, if a subject had an event (No. 2, No. 5 or No. 6), the earliest event date will be used.
2. If a subject did not have PD or death, the censoring date will be the earliest censoring date if the subject met multiple censoring criteria (No. 1, No. 3, No. 4, or No. 7).

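### The PFS missed-visit rule in SAP 8.4 can discard an on-schedule progression that follows an already closed scan gap, and it gives two different censoring dates for that subject

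*SAP*

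**What the plan says.** The rule sits in three parts of SAP 8.4.

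- **Table 4, No. 7.** The situation is "Death or progression after more than one missed visit", with a separate 28-day clause that is not at issue here. The outcome is censoring, dated "Date of last adequate radiologic assessment before missed tumor assessments".
- **Footnote \*\* to Table 4.** "More than 1 missed visits is defined as having either 1 of the following 2 durations being longer than 18 weeks - 1 day", which the SAP converts to 125 days. Duration (a) is "Duration between 2 consecutive tumor assessments". Duration (b) is "Duration between the last adequate tumor assessment and death or PD".
- **Priority list.** Item 1, for subjects with PD or death, takes No. 1, No. 4, No. 8 and No. 7 in turn. For No. 7, "the subject will be censored on the date of the last tumor assessment before PD or death". Only then comes the event step: "Otherwise, if a subject had an event (No. 2, No. 5 or No. 6), the earliest event date will be used". Item 2, for subjects with neither PD nor death, says that "the censoring date will be the earliest censoring date if the subject met multiple censoring criteria", and No. 7 is among the criteria it lists.

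Scans are due every 8 weeks from randomization (SAP 3.2). PFS is a secondary endpoint with a stratified log-rank test at alpha 0.05 (SAP 5.4.2). Duration of response takes its censoring from the PFS rules (SAP 5.4.3; Protocol 9.7.1.6.3).

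**The concern.** A missed-visit rule exists because a progression first seen after a long unobserved interval cannot be dated. That reason disappears once a later scan shows no progression: the subject is then known to have been progression-free through the gap, and a progression found at a later scheduled visit is dated as well as any other.

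Duration (a) ignores this. One closed gap early in follow-up is enough to bring No. 7 into play for the rest of that subject's follow-up. A correctly dated event is then removed from the log-rank test and the Cox model. Because the censoring date is stated in two incompatible ways, two programmers could each follow the SAP and build different PFS datasets.

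**Working it through.** **1. The threshold.** ((8+1) × 2 × 7) − 1 = 125 days, as the SAP states. Nominal intervals with 0, 1 and 2 missed scans are 56, 112 and 168 days, so 125 days does separate one missed scan from two. The figure is sound; the difficulty is which intervals it is applied to.

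**2. What duration (a) adds.** Duration (b) already covers the interval ending in PD or death. What (a) adds is earlier intervals, including those closed by a scan without progression.

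**3. A worked subject.** On treatment throughout, with no new anticancer therapy, so Nos. 1, 4 and 8 do not apply. Scans at Week 8 (day 56), then Weeks 32, 40 and 48 (days 224, 280, 336), all stable disease; Weeks 16 and 24 missed. The gap is 224 − 56 = 168 days, over 125. The next scan is on schedule at Week 56 (day 392).

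| Rule followed | PD at Week 56 | No PD at Week 56, then cutoff |
|---|---|---|
| Table 4 alone | Censored Week 8 (No. 7) | Censored Week 56 (No. 3) |
| Priority list | Censored Week 48 (item 1) | Censored Week 8 (item 2, if No. 7 is applied with its Table 4 date) |
| Table 4 date for No. 7, plus item 2 | Censored Week 8 | Censored Week 8 |
| Rule limited to the interval just before PD or death | Event at Week 56 | Censored Week 56 |

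Under none of the first three rows is the Week 56 progression an event. For the subject with PD, the two stated dates differ by 48 − 8 = 40 weeks. In the first two rows the date depends on what happens at Week 56, although the history up to Week 48 is identical. In the third row it does not, but the SAP does not direct that combination.

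**4. Size.** Inputs from the documents: 152 subjects; 8-weekly scans; median PFS 18.3 months (Study 303, Protocol 7.1); time on treatment 6 to 42 months (Protocol Synopsis), used here as the follow-up range. Assumptions: exponential PFS, uniform follow-up over that range, progression detected at the next attended scan, no treatment discontinuation, and the miss rates below. About 82 to 83 progressions are observed per trial.

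| Chance of missing a scan | Chance of missing the next after a miss | On-schedule progressions lost |
|---|---|---|
| 3% | 3% (independent) | about 0.3 |
| 5% | 5% (independent) | about 0.7 |
| 10% | 10% (independent) | about 2.6 |
| 3% | 30% | about 2.4 |
| 5% | 30% | about 4 |
| 10% | 50% | about 9 |

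With an assumed 1.5% per month discontinuation, the 5%/30% case falls from about 4 to about 2.8. Progression-free subjects with an already closed gap number about 7 in the 5%/30% case and about 20 in the 10%/50% case. They matter only if No. 7 is applied under priority item 2.

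A simpler parameterization agrees in scale. If 2%, 5%, 10% or 20% of subjects have a single two-visit gap starting after one of the first four scans, about 0.9%, 2.2%, 4.5% or 8.8% of PFS events are lost solely through duration (a).

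**The case against.** The best defense is that No. 7 was meant only for a gap running straight into PD or death. On that reading the two censoring dates coincide, because the last assessment before the missed ones is also the last before PD or death. The 40-week conflict could then be taken as evidence that closed gaps were never meant to count. The defense adds that No. 7 is worded only for death or progression, so its mention in priority item 2 catches nobody, and progression-free subjects fall to No. 3.

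Part of this stands. The narrow reading may well be the intent, and the loss of progression-free time holds only if item 2 overrides the wording of Table 4. But the narrow reading leaves duration (a) redundant beside (b) and leaves the entry in item 2 without effect, so the text does not settle the matter in its favor. A programmer who implements (a) as written will lose the events.

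The objection on size also stands. Two or more lost events is not a floor: at 3–5% misses it requires misses that cluster within a subject. Nor do the documents rank PFS above other secondary endpoints; it is listed first, and SAP 5.3.3 gives multiplicity as not applicable.

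**Conclusion.** As written, SAP 8.4 removes on-schedule progressions that follow a closed gap of more than 125 days, for subjects not already censored by Nos. 1, 4 or 8, and it states two incompatible censoring dates for them. Both points follow from the text without any assumption. The size does not: of roughly 82 progressions, the loss runs from under 1 (independent misses at 3–5%) to about 9 (10% misses with a 50% chance of missing the next). The documents give no rate with which to narrow that range.

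A reader might infer more than this:

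- **That every subject with a long gap is censored by this rule.** Nos. 1, 4 and 8 come earlier in the list and may act first.
- **That censoring is necessarily informative.** The date depends on later outcome under the priority list (if No. 7 is applied in item 2) or under Table 4 alone, but not if the Table 4 date is combined with item 2. It turns on which of the conflicting passages governs.
- **That the hazard ratio is biased in a known direction.** The same schedule and rule apply to both blinded arms, and nothing in the documents shows that gaps differ by arm.

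PFS and duration of response (exploratory) are affected. ORR24wk, the primary safety endpoint and the sample size are not. The point should be corrected, but it does not threaten the primary conclusions.

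**What to change.** In SAP 8.4:

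1. Apply the missed-visit clause of No. 7 only when the interval of more than 125 days is the one immediately before the PD scan or death. Delete duration (a), or restrict it to the case where the second assessment is the PD assessment.
2. State one censoring date in both Table 4 and priority item 1: the last adequate assessment before that gap.
3. Remove No. 7 from priority item 2, so that a subject without PD or death is not censored before a closed gap.
4. State in SAP 5.4.3 that duration of response follows the same rule.

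A progression first found at the end of a long gap is still censored before the gap, so the purpose of the rule is kept. The 125-day threshold and the 28-day clause need no change for this point. The cost is a few lines of SAP text and programming before database lock, with no new data.

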The Treatment Period for an individual subject will begin at the time of randomization and will end upon completion of the Off-treatment Visit, which will occur within 30 days after the final administration of study drug. Serious adverse events (SAEs) must be captured for 28 days after the last dose of study drug. Subjects will undergo safety and efficacy assessments as defined in the Schedule of Procedures and Assessments (Table 7) and will continue to receive study treatment until disease progression. The Follow-up Period will begin immediately after the Off-treatment Visit and will continue as long as the subject is alive unless the subject withdraws consent, or until the data cutoff for primary analysis. Subjects who discontinue study drug treatment prior to disease progression will continue to be followed according to the Schedule of Procedures and Assessments until documentation of disease progression or initiation of another anticancer treatment. Subjects will be followed every 12 weeks  $\pm$  1 week for survival, PFS2 and all anticancer treatments received (unless this information is not allowed to be provided due to confidentiality) will be recorded until the data cutoff for primary analysis. Subjects who were enrolled prior to implementation of Amendment 03 and who discontinued lenvatinib treatment due to progressive disease or due to an AE were followed for PFS2 and survival until the date that the last subject transitioned to lenvatinib treatment outside the study (the data cutoff date for this group of 41 subjects).

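### SAP 8.4 gives two conflicting PFS censoring rules for subjects who stop treatment without progression; followed as written, the priority list makes censoring depend on the later outcome

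*SAP*

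**What the plan says.** SAP 8.4 sets PFS censoring in two layers, Table 4 and a priority list after it.

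- **Table 4 row 8** covers "Treatment discontinuation for reasons other than PD". The subject is censored at the last scan before stopping, with no condition on what happens later.
- **Table 4 row 7** censors death or progression after more than one missed visit "or after 28 days from the last dose of study treatment". The only date it gives is the last adequate scan before the missed assessments.
- **List item 1** (subjects with PD or death) says: "If PD is reported after the drug discontinuation visit, the subject will be censored at the date of last radiologic assessment before drug discontinuation". PD at the discontinuation visit is exempt, and "If PD occurred within 4 weeks of drug discontinuation, it will be considered PD at the drug discontinuation visit" and counted. Its No. 7 bullet names only missed assessments; in that case "the subject will be censored on the date of the last tumor assessment before PD or death". Everything left falls to the last bullet: "Otherwise, if a subject had an event (No. 2, No. 5 or No. 6), the earliest event date will be used".
- **List item 2** (subjects without PD or death) takes the earliest censoring date "if the subject met multiple censoring criteria (No. 1, No. 3, No. 4, or No. 7". No. 8 is not named.

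Protocol 9.3.3 and 9.5.1.2.4 keep subjects who stop without progression on 8-weekly scans until PD, new therapy or the data cutoff. Protocol 9.7.1.1.2 leaves the PFS censoring rules to the SAP. SAP 5.4.2 specifies one PFS analysis, with a log-rank test at alpha 0.05. The only sensitivity analysis labelled as such in the SAP's efficacy section concerns overall ORR (SAP 5.4.1). Duration of response takes over the PFS censoring rules (SAP 5.4.3; Protocol 9.7.1.6.3).

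**The concern.** Two programmers working from SAP 8.4 could derive different PFS data for the same subject and both be following the text. The dataset specification is a separate document (SAP 9), not available here; whatever it says, the SAP text that it implements gives two answers.

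The second problem is one of validity. If the list is followed as written, two subjects who stop on the same day are handled differently because of what happens afterwards. The one who progresses late is censored back to before stopping. The one who stays event-free remains in the risk set until the last scan before cutoff. Person-time after stopping is then kept mainly for subjects known not to have progressed, and PFS is overstated. If stopping differs by arm, the hazard ratio shifts as well, and tolerability by arm is what this trial is designed to compare.

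No prespecified PFS or duration-of-response analysis counts PD found more than 4 weeks after stopping, although the scans that would show it are collected.

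**Working it through.** **The plan's own figure.** The threshold for more than one missed visit reproduces: ((8 + 1) × 2 × 7) − 1 = 125 days.

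**Worked subjects.** Scans fall every 56 days (days 56, 112, 168, 224, …). The last dose is on day 200, without PD. No scan is missed, there is no new therapy, and cutoff is day 460. The last scan before stopping is on day 168.

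| Course after stopping | Table 4 row 8 | Priority list |
|---|---|---|
| (a) No PD or death; last scan day 448 | Censored day 168 | Censored day 448 (item 2, No. 3) |
| (b) Clean scans days 224 and 280; death day 300 | Censored day 168 | Event day 300 |
| (c) PD at the day 224 scan | Censored day 168 | Event |
| (d) PD at the day 336 scan | Censored day 168 | Censored day 168 |

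- (a) Both rules censor, but 448 − 168 = 280 days apart. The gap is specific to this example.
- (b) The death is 300 − 200 = 100 days after the last dose, so row 7 also censors it. Row 7 gives no usable date, because no scan was missed (300 − 280 = 20 days, below 125). Reading the 28-day condition into the list's No. 7 bullet would give a third answer: censored on day 280.
- (c) 224 − 200 = 24 days, inside the list's 4-week allowance. Row 8 has no such exception.
- (d) Table row 8 and list agree. Set beside (a) and (b), the list turns the same stop on day 200 into censoring on day 168, censoring on day 448 or an event on day 300, depending only on what followed.

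**Size: PFS level.** Inputs from the documents: median 18.3 months (Study 303 lenvatinib arm, Protocol 7.1), follow-up 6 to 42 months (taken from time on treatment in the Protocol Synopsis, Duration of Treatment), and 8-weekly scans. Assumptions: exponential event times, cutoff uniform over that range, 5% of events are deaths without PD, no new therapy, unchanged hazard after stopping. A simulation of 400,000 subjects gave these 24-month PFS rates:

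| Share stopping without PD | All PD and deaths | Row 8 | List |
|---|---|---|---|
| 10% | 40.3% | 40.3% | 41.4% |
| 20% | 40.3% | 40.2% | 42.7% |
| 30% | 40.3% | 40.2% | 44.4% |

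The list overstates PFS by 1.1, 2.4 and 4.1 points although stopping is uninformative. Row 8 applied to everyone does not.

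**Size: hazard ratio (18 vs 24 mg).** Same median, follow-up and scans; 10% of first events are deaths; 1,000,000 subjects per arm; unstratified Cox; true hazard ratio 1; unchanged hazard after stopping.

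- Stopping 20% a year on 24 mg and 10% on 18 mg: 1.00 counting all events, 1.00 by row 8, 1.058 by the list.
- Arms reversed: 0.945 by the list.
- Stopping 15% a year in both arms: 1.00 throughout.

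**Events moved by the conflict, per 152.** Row 8 against list: 73.9 − 72.0 = 1.9 with unchanged hazard, and 75.2 − 72.1 = 3.1 if the hazard triples after stopping.

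**Sampling error.** With D events the 95% interval around a hazard ratio of 1 is exp(±1.96 × 2/√D): 0.65 to 1.53 for D = 84, and 0.63 to 1.58 for D = 73. The shift ln(1.058) = 0.056 is about a quarter of the standard error 2/√73.9 = 0.233.

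**The case against.** The strongest reply is that item 2 is only a tie-break for subjects who meet several criteria, and does not switch off row 8, which is unconditional. The omission of No. 8 may be an oversight: item 2 does cite No. 7, which by its wording needs a death or progression that these subjects do not have. On that reading event-free stoppers are also censored at the last scan before stopping, the contrast between (a) and (d) disappears, and the hazard ratio in the 20% vs 10% example lies only about 2% from 1. This stands as a possible reading, so outcome-dependent censoring is a consequence of the list as written and not a certainty about the analysis. The death and 4-week conflicts remain either way.

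It can also be said that the 4-week sentence is a specific refinement that governs row 8. That is reasonable for case (c), but it does not settle (a) or (b).

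A third reply is that censoring at treatment stop is a permitted choice for a secondary endpoint, and that SAP 5.8 allows further exploratory analyses. The choice is indeed permitted. But an unspecified exploratory analysis is not a prespecified check on it.

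A reader might infer that progression on about days 29 to 37 is an event by the list and censored by row 7, because the Off-treatment Visit is one "which will occur within 30 days after the final administration of study drug" and its scan may come up to a week later. That equates the discontinuation visit in SAP 8.4 with the Off-treatment Visit, which the SAP does not do. It is a reason to define the term, not a demonstrated gap.

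**Conclusion.** The censoring text is wrong as written and should be corrected. Table and list disagree for event-free stoppers, for deaths more than 28 days after the last dose with no missed scan, and for PD within 4 weeks of stopping. They agree on PD later than that. Confidence is high for the conflict, and does not extend to the size or direction of any bias: those rest on assumed stopping rates and hazards after stopping.

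Three stronger conclusions might be drawn and are not supported.

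- That the PFS comparison is biased in a known direction. The list hazard ratio is about 1.06 or 0.95 depending on which arm stops more, and 1.00 if stopping is equal. All of these are within sampling error.
- That the conflict costs a large share of events. In the same simulation with 15% a year stopping in both arms, on-treatment censoring removes 12% to 22% of events compared with counting everything. That is the effect of a choice the protocol leaves to the SAP; the conflict accounts for about 2 to 3 events per 152.
- That the main result is at risk. PFS is secondary and duration of response exploratory; the ORR analysis at 24 weeks and the 152 subjects do not depend on these rules.

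Whether the rules follow the FDA guidance that the SAP cites cannot be judged from the documents.

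**What to change.** Before database lock:

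1. Make rows 7 and 8 and the priority list one rule set with one defined time anchor, either the last dose or a named visit; define the discontinuation visit if it is kept. State whether a death more than 28 days after the last dose is an event or censored, and on which date when no scan was missed. State whether the 4-week allowance applies. Apply No. 8 in the same way whether or not the subject later progresses, which means naming it in item 2 if it is kept.
2. Prespecify one sensitivity analysis of PFS (same stratified log-rank and Cox) and of duration of response (same Kaplan-Meier summary). It should count all documented PD and deaths up to data cutoff regardless of discontinuation, and keep the new-therapy and missed-visit rules.

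The cost is a text correction to SAP 8.4, one extra derivation and one extra table, all from data already collected and without a protocol amendment. The downside is two PFS estimates to discuss if they differ. Settling the text before unblinding also avoids a choice between readings once the results are known.
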